2. **Informed Consent:** Must be obtained prior to undergoing any study specific procedures. May be collected more than 28 days prior to study entry. As part of the consenting process, participants will be informed of the potential occurrence of immune related adverse events and will be provided with a Patient Information Card.
3. **Tumor History:** Will be collected within 28 days prior to study entry. Includes details of primary diagnosis and treatment history. If available, historical PSA results and imaging assessments (eg, CT scans, MRIs or bone scans) may also be requested.
4. **Medical History:** Includes history of disease process other than prostate cancer (active or resolved) and significant concurrent illness. Includes prior treatments and any current medical treatment for any condition.
5. **Complete and abbreviated physical examinations:** A neurologic examination must be conducted at Screening to look for potential signs suggestive of autoimmune disorders. In addition, all abbreviated physical examinations conducted during Cycle 1 must include a neurologic examination.
6. **Vital signs:** Includes temperature and blood pressure (BP) to be recorded in the seated position after approximately 5 minutes of rest.
7. **Performance status:** Use Eastern Cooperative Oncology Group (ECOG) – see [Appendix 2](#).
8. **Gleason score:** The Gleason score at the time of initial diagnosis and/or time of most current recurrence should be collected.

9. **Unique Screening Labs:** To include hepatitis B surface antigen, hepatitis B core antibody, hepatitis C antibody, and human immunodeficiency virus (HIV). Samples will be analyzed locally.
10. **Hematology:** Complete blood count (CBC) to include hemoglobin, platelets, WBC, neutrophils, lymphocytes, monocytes, eosinophils, and basophils. If baseline assessment was performed within 72 hours of Cycle 1 Day 1, repeat is not required. Samples will be analyzed locally.
11. **Blood Chemistry:** Should include sodium, potassium, chloride, bicarbonate or carbon dioxide, BUN (or urea), uric acid, creatinine, glucose, calcium, magnesium, phosphorus, albumin, total protein, aspartate aminotransferase (AST/SGOT), alanine aminotransferase (ALT/SGPT), alkaline phosphatase, total bilirubin, amylase, lipase, and **CCI** [REDACTED]. If baseline assessment was performed within 72 hours of Cycle 1 Day 1, repeat is not required. Samples will be analyzed locally.

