- Medical History:** Includes history of disease process other than prostate cancer (active or resolved) and significant concurrent illness. Includes prior treatments and any current medical treatment for any condition.
- Complete and abbreviated physical examinations:** A neurologic examination must be conducted at Screening to look for potential signs suggestive of autoimmune disorders. In addition, all abbreviated physical examinations conducted during Cycle 1 must include a neurologic examination.
- Vital signs:** Includes temperature and blood pressure (BP) to be recorded in the seated position after approximately 5 minutes of rest.
- Performance status:** Use Eastern Cooperative Oncology Group (ECOG) – see [Appendix 2](#).
- Gleason score:** The Gleason score at the time of initial diagnosis and/or time of most current recurrence should be collected.
- Unique Screening Labs:** To include hepatitis B surface antigen, hepatitis B core antibody, hepatitis C antibody, and human immunodeficiency virus (HIV). Samples will be analyzed locally.
- Hematology:** Complete blood count (CBC) to include hemoglobin, platelets, WBC, neutrophils, lymphocytes, monocytes, eosinophils, and basophils. If baseline assessment was performed within 72 hours of Cycle 1 Day 1, repeat is not required. Samples will be analyzed locally.

11. **Blood Chemistry:** Should include sodium, potassium, chloride, bicarbonate or carbon dioxide, BUN (or urea), uric acid, creatinine, glucose, calcium, magnesium, phosphorus, albumin, total protein, aspartate aminotransferase (AST/SGOT), alanine aminotransferase (ALT/SGPT), alkaline phosphatase, total bilirubin, amylase, lipase, and CCI [REDACTED]. If baseline assessment was performed within 72 hours of Cycle 1 Day 1, repeat is not required. Samples will be analyzed locally.
12. **Coagulation:** Should include Prothrombin Time (PT) or International Normalized Ratio (INR) and Partial Thromboplastin Time (PTT). Samples will be analyzed locally.
13. **Urinalysis:** Dipstick is acceptable. Microscopic analyses if dipstick abnormal. Samples will be analyzed locally.
14. **Triplicate 12 leads ECGs:** At each time point, three consecutive 12-lead ECGs will be performed approximately 2 minutes apart to determine mean QTcF interval. If the mean QTcF is prolonged (>500 msec), the ECGs should be re-evaluated by a qualified person at the institution for confirmation. Additional triplicate ECGs may be performed as clinically indicated.

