#### 5.4.4.3. PF-06801591 Dose Reductions

Events including, but not limited to, pneumonitis, colitis, creatinine and liver function test (LFT) elevation should be monitored carefully with this class of agents. Changes in the dose levels for PF-06801591 may be allowed depending on the type and severity of toxicity encountered. Dose reductions may be required for PF-06801591, tremelimumab or potentially both compounds depending on the event and the severity. After a dose interruption, it is acceptable to resume dosing with the PrCa VBIR alone, and PF-06801591 treatment to resume at the next planned dosing. Dose reductions of PF-06801591 by 1 dose level may be allowed, including dose reductions below the starting dose. In addition an intermediate dose may be considered. All dose modifications/adjustments must be clearly documented in the participant's source notes and CRF.

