#### 7.1.2. Laboratory Safety Assessment

Hematology, blood chemistry and coagulation will be drawn at the time points described in the [Schedule of Activities](#) and analyzed at local laboratories.

Hematology	Chemistry	Coagulation	Urinalysis
Hemoglobin	ALT	PT or INR	Urine dipstick for urine protein: If positive collect 24-hr and microscopic (Reflex Testing)
Platelets	AST	PTT	
WBC	Alk Phos		
Absolute Neutrophils	Sodium		
Absolute Lymphocytes	Potassium		
Absolute Monocytes	Magnesium		Urine dipstick for urine blood: If positive collect a microscopic (Reflex Testing)
Absolute Eosinophils	Chloride		
Absolute Basophils	Total Calcium		
	Total Bilirubin 		
	BUN or Urea		
	Creatinine		
	Uric Acid		
	Glucose (non-fasted)		
	Albumin		

Hematology	Chemistry	Coagulation	Urinalysis
	Phosphorous or Phosphate		
	Lactate dehydrogenase		
	Lipase		
	Amylase		
	Bicarbonate or carbon dioxide		
	Total protein		
	TSH (if abnormal, reflex free T4 and free T3 tests) 		

1. For Hy's law potential cases, in addition to repeating AST and ALT, laboratory tests should include albumin, creatine kinase, total bilirubin, direct and indirect bilirubin, gamma-glutamyl transferase, prothrombin time (PT)/INR, alkaline phosphatase, total bile acids and acetaminophen drug and/or protein adduct levels.
2. For participants in Cohorts 6A through 9A and Cohorts 3B and 5B.

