### **8.6.2. Potential Cases of Drug-Induced Liver Injury**

Liver Function Tests (LFTs) are not required as a routine safety monitoring procedure in this study. However, should an investigator deem it necessary to run LFTs because of clinical sign/symptom presentation in a patient, such LFT results should be handled and followed up as described below.

Abnormal values in aspartate aminotransferase (AST) and/or alanine aminotransferase (ALT) levels concurrent with abnormal elevations in total bilirubin level that meet the criteria outlined below in the absence of other causes of liver injury are considered potential cases of drug-induced liver injury (potential Hy's law cases) and should always be considered important medical events.

The threshold of laboratory abnormalities for a potential case of drug-induced liver injury depends on the patient's individual baseline values and underlying conditions. Patients who present with the following laboratory abnormalities should be evaluated further to definitively determine the etiology of the abnormal laboratory values:

- Patients with AST or ALT and total bilirubin baseline values within the normal range who subsequently present with AST or ALT values  $\geq 3$  times the upper limit of normal ( $\times$  ULN) concurrent with a total bilirubin value  $\geq 2 \times$  ULN with no evidence of hemolysis and an alkaline phosphatase value  $\leq 2 \times$  ULN or not available;
- For patients with preexisting ALT **OR** AST **OR** total bilirubin values above the ULN, the following threshold values should be used in the definition mentioned above:
- For patients with preexisting AST or ALT baseline values above the normal range: AST or ALT value  $\geq 2$  times the baseline values and  $\geq 3 \times$  ULN, or  $\geq 8 \times$  ULN (whichever is smaller).

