### **Concurrent with**

- For patients with pre-existing values of total bilirubin above the normal range: Total bilirubin level increased from baseline by an amount of at least  $1 \times$  ULN **or** if the value reaches  $\geq 3 \times$  ULN (whichever is smaller).

The patient should return to the investigational site and be evaluated as soon as possible, preferably within 48 hours from awareness of the abnormal results. This evaluation should include laboratory tests, detailed history, and physical assessment. The possibility of hepatic neoplasia (primary or secondary) should be considered. In addition to repeating measurements of AST and ALT, laboratory tests should include albumin, creatine kinase, total bilirubin, direct and indirect bilirubin, gamma-glutamyl transferase, prothrombin time (PT)/international normalized ratio (INR), and alkaline phosphatase. A detailed history, including relevant information, such as review of ethanol, acetaminophen, recreational drug, and supplement consumption, family history, occupational exposure, sexual history, travel history, history of contact with a jaundiced person, surgery, blood transfusion, history of liver or allergic disease, and work exposure, should be collected. Further testing for acute hepatitis A, B, or C infection and liver imaging (eg, biliary tract) may be warranted. All cases confirmed on repeat testing as meeting the laboratory criteria defined above, with no other cause for LFT abnormalities identified at the time, should be considered potential Hy's law cases irrespective of availability of all the results of the investigations performed to determine etiology of the abnormal LFTs. Such potential Hy's law cases should be reported as SAEs.

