Grade 2 Mild to moderate new symptoms.	
 
-Withhold study treatment.
 
-Pulmonary and Infectious Disease consults.
 
-Monitor symptoms daily; consider hospitalization.
 
-1.0 to 2.0 mg/kg/day prednisone or equivalent.
 
-Add prophylactic antibiotics for opportunistic infections.
 
-Consider bronchoscopy, lung biopsy.
 
	
 
-Re-assess every 1 to 3 days If improves:
 
-When symptoms return to Grade <math>\leq 1</math>, taper steroids over at least 1 month, and then resume study treatment following steroids taper.
 
-If not improving after 2 weeks or worsening: Treat as Grade 3 to 4.
 

Grade 3 to 4 Grade 3: Severe new symptoms; New/worsening hypoxia; Grade 4: Life-threatening.	
 
-Permanently discontinue study treatment.
 
-Hospitalize.
 
-Pulmonary and Infectious Disease consults.
 
-1.0 to 2.0 mg/kg/day prednisone or equivalent.
 
-Add prophylactic antibiotics for opportunistic infections.
 
-Consider bronchoscopy, lung biopsy.
 
	
 
-If improves to Grade <math>\leq 1</math>:
 
-Taper steroids over at least 1 month.
 
-If not improving after 48 hours or worsening: Add additional immunosuppression (for example, infliximab, cyclophosphamide, IV immunoglobulin, or mycophenolate mofetil).
 

Hepatic irAEs		
Grade of Liver Test Elevation (NCI-CTCAE v4)	Initial Management	Follow-up Management
Grade 1 Grade 1 AST or ALT > ULN to 3.0 x ULN and/or Total bilirubin > ULN to 1.5 x ULN.	-Continue study treatment.	-Continue liver function monitoring. -If worsens: Treat as Grade 2 or 3 – 4.
Grade 2 AST or ALT >3.0 to ≤5 x ULN and/or total bilirubin >1.5 to ≤3 x ULN.	-Withhold study treatment.  -Increase frequency of monitoring to every 3 days.	-If returns to Grade ≤1: -Resume routine monitoring; resume study treatment.  -If elevation persists >5 to 7 days or worsens: -Treat as Grade 3 to 4.

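### Protocol Section 8.6.2 calls liver function tests non-routine and introduces its Hy's law rules only for symptom-prompted tests, although every scheduled chemistry panel contains them

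*Protocol*

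**What the plan says.** Protocol Section 8.6.2 (Potential Cases of Drug-Induced Liver Injury) opens with "Liver Function Tests (LFTs) are not required as a routine safety monitoring procedure in this study". Its second sentence sets the context for what follows: "should an investigator deem it necessary to run LFTs because of clinical sign/symptom presentation in a patient, such LFT results should be handled" as the section then describes. The section goes on to give the Hy's law thresholds, a return visit preferably within 48 hours of learning of the abnormal result, the history and examination to be taken, and the reporting rule "Such potential Hy's law cases should be reported as SAEs".

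Elsewhere the protocol schedules these tests:

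- Footnote 11 (Blood Chemistry) of the Schedule of Activities for the expansion cohorts lists "aspartate aminotransferase (AST/SGOT), alanine aminotransferase (ALT/SGPT), alkaline phosphatase, total bilirubin, amylase, lipase". The escalation schedule and both maintenance schedules list the same analytes.
- Section 7.1.2 has chemistry drawn at the scheduled time points, and its table includes ALT, AST, alkaline phosphatase and total bilirubin. Footnote 1 to that table adds: "For Hy's law potential cases, in addition to repeating AST and ALT, laboratory tests should include albumin, creatine kinase, total bilirubin", among others.
- Section 5.4.4.3 says: "Events including, but not limited to, pneumonitis, colitis, creatinine and liver function test (LFT) elevation should be monitored carefully with this class of agents".
- Table 6 and the hepatic table in Appendix 7 act on AST, ALT and bilirubin by grade. Appendix 7 Grade 2 is "AST or ALT >3.0 to ≤5 x ULN and/or total bilirubin >1.5 to ≤3 x ULN".

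**The concern.** The opening statement of 8.6.2 contradicts the testing schedule and the dose-modification rules. It reads like template text that was not adapted to this study.

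The contradiction matters because of the second sentence. If the rules cover only tests prompted by signs or symptoms, they do not cover an asymptomatic elevation found on a scheduled draw. In a trial with chemistry at nearly every visit, that is how most such elevations would be found.

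The Hy's law thresholds, the recall time, the etiology history and the explicit SAE rule appear only in 8.6.2. Two sites with the same laboratory result could therefore report it differently. SAE status brings sponsor notification within 24 hours (Section 8.14.1). The trial has no external monitoring committee, and the internal review relies partly on SAE surveillance (Section 9.7).

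**Working it through.** There is no sample size, power or event count to reproduce. The check compares the texts and then tests whether another section fills the gap.

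**Step 1. Are LFTs routine in this protocol?** Yes. AST, ALT, alkaline phosphatase and total bilirubin are in the chemistry panel of the expansion, escalation and both maintenance schedules, and in the Section 7.1.2 table. Chemistry is scheduled from screening through treatment, maintenance and follow-up. No reading makes the first sentence of 8.6.2 correct.

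**Step 2. Does 8.6.2 limit itself to symptom-prompted tests?** It is ambiguous. The introductory sentence refers to tests ordered because of signs or symptoms and applies the rules to those results. The later paragraphs have no such limit: qualifying elevations are always important medical events, and the reporting rule covers all cases confirmed on repeat testing.

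**Step 3. Where does each element of the response appear?**

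| Element | 8.6.2 | 7.1.2 footnote 1 | Table 6 | Appendix 7, hepatic |
|---|---|---|---|---|
| Hy's law thresholds | Yes | No (uses the term without defining it) | No | No |
| Additional laboratory tests | Yes | Yes | No | No such list |
| Recall, preferably within 48 hours | Yes | No | No | No |
| Etiology history | Yes | No | No | No |
| Explicit SAE rule | Yes | No | No | No |
| Hold or stop dosing by grade | No | No | Yes | Yes |

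**Step 4. Does grade-based management catch the same cases?** Assume normal baseline values, alkaline phosphatase at most 2 x ULN (or not available) and no hemolysis.

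- 8.6.2 criterion: AST or ALT >= 3 x ULN and bilirubin >= 2 x ULN.
- Appendix 7 Grade 2: AST or ALT > 3.0 to <= 5 x ULN and/or bilirubin > 1.5 to <= 3 x ULN.
- Overlap: AST or ALT > 3 to <= 5 x ULN with bilirubin 2 to 3 x ULN.
- Example: ALT 4 x ULN, bilirubin 2.5 x ULN. 4 >= 3 and 2.5 >= 2, so 8.6.2 is met. 4 <= 5 and 2.5 <= 3, so the case is Grade 2 in Appendix 7.

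For that case Appendix 7 withholds treatment, tests every 3 days and resumes at Grade 1 or lower. It moves to Grade 3 to 4 management if the elevation persists beyond 5 to 7 days or worsens. Table 6 also withholds at Grade 2. Neither gives a recall time or an SAE rule.

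**Step 5. Do these tests turn abnormal here?** Section 1.3.2 reports treatment-related ALT increase in 8 of 69 participants (8/69 = 11.6%) and AST increase in 7 of 69 (7/69 = 10.1%). It does not say whether any of them also met the bilirubin criterion.

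**The case against.** The strongest reply is that a sensible reader would apply 8.6.2 to scheduled results anyway. The threshold paragraph speaks of any patient with the listed abnormalities, and the recall is timed from awareness of the result, not from symptoms. No sentence exempts scheduled tests. Footnote 1 of Section 7.1.2 is attached to total bilirubin in the routine panel and uses a term defined only in 8.6.2, so following it leads back to the 8.6.2 criteria. It also preserves the laboratory part of the work-up.

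There are further safeguards on seriousness. Section 8.6 has important medical events reported as serious. Section 8.5 makes a result that needs further diagnostic testing an AE. Section 8.1 lets the sponsor upgrade a non-serious AE. Section 9.7 provides internal review of individual data. The 48-hour recall is itself only a preference, and the Part B cohorts are fully enrolled (Section 3.1.2), so a change helps only participants still on treatment or in follow-up.

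Much of this stands. Many investigators would apply the rules, and the practical gap is small. But the safeguards either depend on 8.6.2 or rest on judgment. The statement that Hy's law cases are always important medical events sits inside 8.6.2, under the limiting introduction, and Section 8.6.1 says there are no protocol-specified SAEs. None of the other sections supplies the thresholds, the recall time or the explicit SAE rule. Closed enrollment does not remove the need: treatment can continue until progression, refusal or unacceptable toxicity, followed by 6 months of follow-up, with chemistry scheduled throughout.

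**Conclusion.** The concern holds. The first sentence of 8.6.2 is wrong as written, and the second leaves it unclear whether the Hy's law rules cover asymptomatic elevations found on scheduled tests. That the contradiction exists is certain; that a site would act on the narrow reading is only a possibility.

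The consequence is limited. Elevations would still be detected and dosing still managed. What could be lost is the recall, the etiology history and consistent SAE reporting, most clearly for cases with AST or ALT > 3 to 5 x ULN and bilirubin 2 to 3 x ULN. That range assumes normal baseline values and the alkaline phosphatase and hemolysis conditions of 8.6.2. The effect on the safety endpoint is confined to the SAE tabulations in Section 9.5.1; the laboratory-abnormality tabulations do not depend on 8.6.2. The number of cases affected cannot be derived from the documents and may be zero. This is a wording inconsistency that should be corrected. It does not threaten the trial.

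**What to change.** Replace the first two sentences of Protocol Section 8.6.2 with:

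> LFTs (AST, ALT, alkaline phosphatase, total bilirubin) are part of the scheduled chemistry panel. The criteria, evaluation and SAE reporting below apply to every AST, ALT and bilirubin result, scheduled or unscheduled, regardless of symptoms.

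The rest of the section can stay as it is. The cost is two sentences in the next amendment, with no new tests or visits.

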### **Concurrent with**

- For patients with pre-existing values of total bilirubin above the normal range: Total bilirubin level increased from baseline by an amount of at least  $1 \times$  ULN **or** if the value reaches  $\geq 3 \times$  ULN (whichever is smaller).

The patient should return to the investigational site and be evaluated as soon as possible, preferably within 48 hours from awareness of the abnormal results. This evaluation should include laboratory tests, detailed history, and physical assessment. The possibility of hepatic neoplasia (primary or secondary) should be considered. In addition to repeating measurements of AST and ALT, laboratory tests should include albumin, creatine kinase, total bilirubin, direct and indirect bilirubin, gamma-glutamyl transferase, prothrombin time (PT)/international normalized ratio (INR), and alkaline phosphatase. A detailed history, including relevant information, such as review of ethanol, acetaminophen, recreational drug, and supplement consumption, family history, occupational exposure, sexual history, travel history, history of contact with a jaundiced person, surgery, blood transfusion, history of liver or allergic disease, and work exposure, should be collected. Further testing for acute hepatitis A, B, or C infection and liver imaging (eg, biliary tract) may be warranted. All cases confirmed on repeat testing as meeting the laboratory criteria defined above, with no other cause for LFT abnormalities identified at the time, should be considered potential Hy's law cases irrespective of availability of all the results of the investigations performed to determine etiology of the abnormal LFTs. Such potential Hy's law cases should be reported as SAEs.

### **8.7. Hospitalization**

Hospitalization is defined as any initial admission (even less than 24 hours) in a hospital or equivalent healthcare facility or any prolongation of an existing admission. Admission also includes transfer within the hospital to an acute/intensive care unit (eg, from the psychiatric wing to a medical floor, medical floor to a coronary care unit, or neurological floor to a

tuberculosis unit). An emergency room visit does not necessarily constitute a hospitalization; however, the event leading to the emergency room visit should be assessed for medical importance.

Hospitalization does not include the following:

- Rehabilitation facilities;
- Hospice facilities;
- Respite care (eg, caregiver relief);
- Skilled nursing facilities;
- Nursing homes;
- Same-day surgeries (as outpatient/same day/ambulatory procedures).

Hospitalization or prolongation of hospitalization in the absence of a precipitating, clinical AE is not in itself an SAE. Examples include:

- Admission for treatment of a preexisting condition not associated with the development of a new AE or with a worsening of the preexisting condition (eg, for workup of persistent pre-treatment laboratory abnormality);
- Social admission (eg, patient has no place to sleep);
- Administrative admission (eg, for yearly physical examination);
- Protocol-specified admission during a study (eg, for a procedure required by the study protocol);
- Optional admission not associated with a precipitating clinical AE (eg, for elective cosmetic surgery);
- Hospitalization for observation without a medical AE;
- Preplanned treatments or surgical procedures. These should be noted in the baseline documentation for the entire protocol and/or for the individual patient;
- Admission exclusively for the administration of blood products.

Diagnostic and therapeutic noninvasive and invasive procedures, such as surgery, should not be reported as AEs. However, the medical condition for which the procedure was performed should be reported if it meets the definition of an AE. For example, an acute appendicitis that begins during the AE reporting period should be reported as the AE, and the resulting appendectomy should be recorded as treatment of the AE.

